5.3.3 Summary Statistics

Data will be summarised by means of summary statistics. For continuous data the following summary statistics will be presented: number of observations, mean value, standard deviation, minimum, first quartile, median, third quartile and maximum value. Categorical data will be presented as counts and percentages. The data will be presented by visit. Baseline, demographics, primary endpoint, and key secondary endpoints will also be summarised by region.

Summary statistics will be presented by treatment group and assessment time and/or visit, as applicable.

5.3.4 Subject Data Listings

Data collected in the eCRF, as well as any derived assessments used for statistical analyses, will generally be listed in Appendix 16.2 (see section 7.2). eCRF check questions [e.g. lab samples taken (Yes/No)] and reminders may not be listed. Listings will primarily be sorted by centre, subject-number and visit and/or any other natural ordering related to the applicable assessment.

In CRF modules where a date is recorded, the date and the relative day (in relation to date of randomisation) will be printed in the corresponding listing. In modules where both a start date and stop date is recorded, also a duration will be included in the listings.

5.3.5 Demographic and other Baseline Characteristics

A subject disposition will be produced, including number of subjects screened, randomised, withdrawn from trial (with reason for withdrawal), number of subjects withdrawing from treatment but remaining in trial, number of subjects completing double-blind treatment period and follow-up, number of subjects included in the safety analysis, full analysis and per protocol sets. Demographics, standard baseline characteristics and aPAP history data will be presented using summary statistics. Data that is measured both before baseline and at other visits following randomisation will in general be presented in other sections in by visit displays.

5.3.6 Primary Efficacy analysis

The primary efficacy variable, (A-a)DO₂, will be collected at Screening, Baseline (randomisation), Week 4, 12 and 24 during treatment period, and at Week 12, 24, 36 and 48 during the follow-up period. All (A-a)DO₂ values reported in the CRF will be recalculated for statistical analyses using the equation:

$$Aa\ Gradient = \left(F_i O_2 (P_{atm} - P_{H_2O}) - \frac{P_a CO_2}{0.8} \right) - P_a O_2$$

where F_iO₂ is fraction of inspired oxygen

P_{atm} is ambient atmospheric pressure

P_{H₂O} is saturated vapour pressure of water at body temperature (set to 47 mmHg / 6.266 kPa)

P_aCO₂ is arterial partial pressure of carbon dioxide

P_aO₂ is arterial partial pressure of oxygen

Any of these assessments reported in kPa will be converted to a result in mmHg before the calculations, this will be done using a factor k=7.5.

The primary efficacy endpoint, absolute change from baseline of (A-a)DO₂ after 24-weeks treatment, will be analysed based on an ANCOVA model including treatment group, WLL (stratification), Japan vs other countries, and baseline (A-a)DO₂. The data from the three treatment groups will be analysed all together (all treatment groups included in one model). Contrasts will be set up to estimate treatment differences in change from baseline with 95% confidence intervals (CI) and the corresponding p-value for Molgramostim OD vs. Placebo and for Molgramostim intermittently vs. Placebo.

For each analysis two sided tests will be performed where the null hypothesis is that there is no difference between treatment groups, which will be tested against the alternative that

there is a difference. Control for type-1 error inflation due to multiple testing will be handled as described in section 5.4.

A de-facto estimand approach will be applied, where for the primary analysis, all observed data will be included, irrespective of subject adherence to the randomised treatment. Subjects who withdraw from their randomised treatment before week 24 will be followed up through to week 24, and their week 24 data will be considered as primary, irrespective of treatment discontinuation, treatment interruption(s), use of rescue medication (WLL or other), etc.

All assessed (A-a)DO₂ measurements, and the corresponding changes from baseline will be summarised by visit and treatment group. In addition, similar summaries of (A-a)DO₂ will also be produced excluding data collected during treatment discontinuation, treatment interruption(s) and use of rescue medication (WLL or other). The decision of what data will be excluded and the reason will be identified during the blind review of data and documented in the "Pre-analysis-review"-document before data base lock (DBL).

Mean profiles for (A-a)DO₂ observed values and change from baseline over time will be provided.

Sensitivity Analyses

The following sensitivity analyses for the primary endpoint will be done in order to evaluate the robustness of the results in relation to influence of any missing data. The sensitivity analyses should be considered supportive analyses and will thus not be part of the procedures applied to control type-1 error rate for testing hypotheses for primary and key secondary efficacy endpoints as described in section 5.4.

- A mixed model for repeated measures (MMRM) will be applied including fixed, categorical effects for treatment, WLL (stratification), visit, treatment-by-visit interaction, Japan vs other countries, and fixed covariates for baseline (A-a)DO₂. An unstructured covariance matrix will be applied to model the within-subject errors, if possible. If this analysis fails to converge, compound symmetry will be tested. Kenward-Roger approximation will be used to estimate denominator degrees of freedom. This methodology does not require imputation of missing data. Instead missing data is modelled based on the subjects' available data and on other subjects' data over time (this approach is valid under assumption that data is missing according to 'Missing at Random' (MAR)) [2].
- Subjects who withdraw from the study early and who do not have week 24 data available will have their (A-a)DO₂ measurement imputed using multiple imputation (MI). This will be done by first ensuring a monotone missing data pattern by imputation of intermediate missing data (baseline, Week 4 and Week 12) by a Markov chain Monte Carlo (MCMC) approach, where imputations are done by treatment group Japan vs other countries, and WLL (stratification) if possible (strata may be dropped depending on the number of observations per combination). The imputation will be done generating 10 data sets. When monotone missingness has been accomplished, then the remaining missing data, up to and including Week 24, will be imputed using a monotone regression approach using treatment and WLL (stratification) as class variables. Each replication of the data, including the imputed missing values, will then be analysed using the ANCOVA used in the primary analysis, and estimates will be pooled using proc MIANALYZE SAS®. (this approach is valid under assumption that data is missing according to MAR).

- If superiority has been determined for any of the comparisons planned for the primary endpoint, a tipping point analysis (TP) will be applied where subjects with a missing endpoint (Week 24) in the group for which superiority has been determined will be assigned progressively worse (A-a)DO₂. This will be done by generating imputed data according to the previous step and using the MNAR option in proc MI SAS® to adjust imputed Week 24 data with an appropriate sized shift parameter in the superior arm in an iterative manner until the results shift from significant (P<0.05) to non-significant (P>0.05). From this analysis, results will be presented including overall estimates at the tipping point, as well as descriptive statistics for imputed data vs non-imputed data.
- A “reasonably worst case” scenario. For the primary analysis, patients in either of the active arms will have the value of the 10th percentile from their dose arm imputed (i.e. approximately the 3rd worst case) whilst patients in the placebo arm will have the median for the placebo arm imputed. This analysis will be based on the same ANCOVA model as applied for the primary analysis.

The above sensitivity analyses can be considered as de-facto approaches. The following sensitivity analyses will also be conducted as de-jure estimation approaches to evaluating data:

- A sensitivity analysis will be done in order to evaluate the robustness of the results due to subjects having WLL, open-label molgramostim or rituximab (rescue treatment). For these subjects, all (A-a)DO₂ measurements following the rescue treatment will be excluded and then re-imputed using multiple imputation (in the same way as described above for imputing data for subjects withdrawn from the study early, and who do not have week 24 data available). These subjects will contribute with their data available prior to the rescue treatment and imputed data following the rescue treatment
- A completer analysis will be done, including only data for subjects who completed the 24 weeks and who did not discontinue treatment. This analysis will be based on the same ANCOVA model as applied for the primary analysis.
- The primary analysis will be repeated for PPS.

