7.2.1.2 Screening (Visit 1)

ACTIVITIES AND ASSESSMENTS:

At Screening (Visit 1), the following activities and assessments will be performed:

- Informed consent (if not done during pre-screening visit period, *Section 7.2.1.1*) - Signed and dated by the subject and by the person who conducted the informed

consent discussion will be collected prior to any trial related procedures described in this protocol (*Section 13.1.3*)

- Eligibility criteria - Assessment of inclusion and exclusion criteria (*Section 8.2* and *Section 8.3*)
- Demographics and Baseline data (*Section 10.3.1*)
- Medical history (*Section 10.3.2*)
- Physical examination (*Section 10.4.3*)
- Vital signs (*Section 10.4.4*)
- (A-a)DO₂ and PaO₂ (*Section 10.1.1*)
- Lung function tests (*Section 10.1.2*)
- 6MWT (*Section 10.1.3*)
- Laboratory safety assessments (haematology and clinical chemistry) (*Section 10.4.6*)
- Serum pregnancy test and instruction in contraceptive measures (*Section 10.5*)
- DSS (*Section 10.1.8*)
- Arrangement for trial drug administration training (*Section 9.1.5*)

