10 TRIAL ASSESSMENTS

10.1 Efficacy Assessments

10.1.1 Blood Gas Analysis

The following variables will be assessed from an arterial blood gas sample at the timepoints shown in *Table 1*:

- (A-a)DO₂ (mmHg/kPa)
- PaO₂ (mmHg/kPa)
- PaCO₂ (mmHg/kPa)

Sites that are experienced in the use of capillary sampling for blood gas analysis as part of their standard care, may use this option instead of an arterial blood gas sample at Screening (Visit 1), Weeks 4 and 12 (Visits 3 and 5) and all Follow-up Visits, but an arterial sample for blood gas is mandatory at Baseline (Visit 2) and Week 24 (Visit 8).

Subjects should rest for at least 10 minutes before puncture and the sample should be taken in supine position. Trial specific instructions will be provided in a separate document. The sample will be analysed in accordance with local routines.

If possible, arterial blood gases at Baseline should be conducted with the subject breathing room air. If the subject cannot tolerate temporary discontinuation of supplemental oxygen during blood gas sampling at Baseline, blood gas sampling at subsequent visits should be conducted using the same oxygen flow rate as was used at Baseline.

The (A-a)DO₂ will be calculated based on PaO₂, PaCO₂ and the ambient atmospheric pressure based on a standard equation (see section 10.2.1).

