5.3.2 Definitions

Baseline	Baseline measurements refers to the last non-missing assessment made before randomisation. If a measurement is intended to be collected at the baseline visit, but is missing, then a corresponding measurement taken at the screening visit may be used to replace the missing assessment at the baseline visit.
Relative day	The relative day of an event is derived as follows: $\text{Relative day} = (\text{Start date}) - (\text{Date of first administration of IMP}) + 1.$ For days before the start date, calculate as $\text{Relative day} = (\text{Start date}) - (\text{Date of first administration of IMP})$. In this way, there will be no day=0. So, Day 1 is the same day as the day of first administration of IMP, and Day -1 is the day before.
(A-a)DO ₂	Alveolar-arterial oxygen difference is a measure of the difference between the alveolar concentration (A) of oxygen and the arterial (a) concentration of oxygen
DLCO	Uptake of carbon monoxide from a single inspiration in standard time.
FEV ₁	The volume of air that can forcibly be blown out in one second, after full inspiration.
FVC	The maximum amount of air a person can expel from the lungs after a maximal inhalation and during a forceful expiration.
SpO ₂	Indirect measurement of oxygen saturation using a finger probe, ear sensor or similar device.
6MWT	Test used to measure the distance that a subject can walk quickly on a flat hard surface in a period of 6 minutes (at an individually predetermined oxygen supplementation).
VC	The maximum amount of air a person can slowly expel from the lungs after a maximum slow inhalation.
% predicted	Calculation of % predicted of spirometry parameters collected during the double-blind period will be made centrally for statistical analysis using the same equation for all sites.
Region	For summaries and figures split by region 'Europe' will include: Denmark, France, Germany, Greece, Italy, Netherlands, Portugal, Russia, Slovakia, Spain, Switzerland and United Kingdom. 'Other' will include: Australia, Israel, South Korea and Turkey while Japan and the United States will be defined as their own regions.

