5.3.7 Secondary Efficacy Analyses

Key Secondary Efficacy Analyses

The following key secondary efficacy endpoints are considered confirmatory endpoints and will therefore be part of the testing procedure in order to control for multiplicity as described in section 5.4.

Absolute change from baseline in 6 minute walking distance and in SGRQ total score after 24-weeks treatment

6 minute walking distance (6MWD)

The 6 minute walking distance (6MWD) is captured as part of the 6 minute walk test (6MWT) (See general description of 6MWT under Further Secondary Efficacy Analyses). Absolute change from baseline in 6 minute walking distance, will be summarized by treatment group and visit. The key secondary endpoint, absolute change from baseline after 24 weeks of treatment, will be analysed as described below.

St Georges Respiratory Questionnaire (SGRQ)

The St Georges Respiratory Questionnaire (SGRQ) is a respiratory specific questionnaire. The symptoms component with 3-month symptoms recall is used. The three domain scores, Symptoms, Activity, and Impacts and the Total score will be calculated. Scores are expressed as a percentage of overall impairment where 100 represents worst possible health status and 0 indicates best possible health status. The standard scoring algorithms will be applied, as described in the St George's Respiratory Questionnaire Manual Version 2.3, June 2009.

The three derived domain scores and total score, and the corresponding changes from baseline will be summarised by treatment group and visit. Individual item responses will only be listed. The key secondary efficacy endpoint, Change from baseline in SGRQ total score after 24-weeks of treatment will be analysed as described below.

Analysis of change from baseline after 24 weeks of treatment in 6 minute walking distance (6MWD) and Total SGRQ

Absolute change from baseline in 6MWD and in SGRQ will be analyzed using the same ANCOVA model as for (A-a)DO₂, including all data irrespective of adherence to treatment regimens as the main approach, and the results from these analyses will be part of the procedures to control for multiple testing (see section 5.4).

Sensitivity analyses for absolute change from baseline in 6MWD and SGRQ will be done using similar approaches as those used for the sensitivity analyses for (A-a)DO₂, but will be limited to:

- Mixed model for repeated measurements (MMRM),
- ANCOVA after multiple imputation,
- ANCOVA completer analysis

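### 6MWD and (A-a)DO2 are measured at both Screening and Baseline, but the confirmatory ANCOVA adjusts only for Baseline; adding the Screening value is a cheap efficiency gain, chiefly for 6MWD, of uncertain size

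*SAP*

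**What the plan says.** SAP 5.3.6 says (A-a)DO2 "will be collected at Screening, Baseline (randomisation), Week 4, 12 and 24 during treatment period". The visit list in Protocol 7.2.1.2, which opens "At Screening (Visit 1), the following activities and assessments will be performed", includes both the blood gas and the 6MWT. Protocol 7.2.1.3 repeats both at Baseline, 14 days (± 7) later, and the flow chart in Protocol 7.2.2 agrees.

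Only one of the two readings reaches the analysis. SAP 5.3.2 reads: "Baseline measurements refers to the last non-missing assessment made before randomisation". Its one stated modelling use for the Screening reading is as a stand-in: if the Baseline value is missing, "then a corresponding measurement taken at the screening visit may be used to replace the missing assessment at the baseline visit".

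The primary endpoint "will be analysed based on an ANCOVA model including treatment group, WLL (stratification), Japan vs other countries", together with baseline (A-a)DO2. For the key secondary endpoints, "Absolute change from baseline in 6MWD and in SGRQ will be analyzed using the same ANCOVA model as for" (A-a)DO2. SAP 5.5 confirms a single baseline covariate. The MMRM and the multiple imputation in SAP 5.3.6 do not use Screening as a further pre-randomisation value either. No reason is given for leaving it out. SGRQ is not measured at Screening, so this point does not touch it.

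**The concern.** One pre-randomisation reading of a variable endpoint is a noisy covariate. A second reading can explain more of the Week 24 variation and shrink the residual variance. Because it is taken before randomisation, it cannot bias the treatment contrast.

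The stake lies mostly with 6MWD. SAP 3.2 and Appendix 2 name it as the critical endpoint in the re-estimation that took the trial from 90 to 135 subjects. That calculation used a two-sided 5% level, whereas SAP 5.4 tests the key secondary endpoints by a truncated Hochberg procedure at ordered levels 0.0417, 0.0229 and 0.0167. A missed key secondary endpoint also cuts the level available for intermittent dosing from 0.05 to 0.0083 or 0.0042.

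**Working it through.** **Inputs from the documents.** 6MWD: residual MSE 4928.203 from an ANCOVA with stratum and one baseline value, 51 subjects, so SD = √4928.203 = 70.2 m; effect 50 m; two-sided 5% (SAP Appendix 2). Final size 45 per arm (SAP 3.2). Primary endpoint: delta 10 mmHg, SD 7.5 mmHg (SAP 3.2).

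**Reproducing the plan's figure.** A two-sample t-test with the noncentral t distribution, delta 50 and SD 70.2, gives 89.7% power at 42 per group and 90.4% at 43. So n = 43 for 90% power, as in Appendix 2 (and 32 for 80%, also matching).

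**Power as planned, 45 per arm.** Noncentrality = 50 / (70.2 × √(2/45)) = 3.38 on 88 degrees of freedom, with all 45 per arm assumed to have Week 24 data. Power is 91.6% at 0.05, about 90% at 0.0417, 85.4% at 0.0229 and 82.4% at 0.0167.

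**Effect of a second covariate.** Let a be the Screening–Baseline correlation, b the Baseline–Week 24 correlation and s the Screening–Week 24 correlation. None is reported; all values below are assumptions. Then

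R² = (b² + s² − 2abs) / (1 − a²), and the variance ratio is VR = (1 − R²) / (1 − b²).

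If s = b this reduces to VR = [1 − 2b²/(1 + a)] / (1 − b²). For a = b = s = 0.7: [1 − 0.98/1.7] / 0.51 = 0.4235/0.51 = 0.83. If Screening predicts Week 24 only through Baseline (s = ab), R² = b² and VR = 1 exactly. The new residual SD is 70.2 × √VR, put back into the same t-test.

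| a | b | s | VR | SD (m) | n per arm, 90% at 0.05 | Power at 0.05 | Power at 0.0167 |
|---|---|---|---|---|---|---|---|
| 0.7 | 0.7 | 0.7 | 0.83 | 64.0 | 36 | 95.6% | 89.5% |
| 0.8 | 0.7 | 0.7 | 0.89 | 66.3 | 38 | 94.2% | 86.9% |
| 0.9 | 0.7 | 0.7 | 0.95 | 68.4 | 41 | 92.9% | 84.6% |
| 0.9 | 0.6 | 0.6 | 0.97 | 69.2 | 42 | 92.4% | 83.7% |
| 0.8 | 0.7 | 0.6 | 0.99 | 69.9 | 43 | 91.9% | 82.8% |
| 0.8 | 0.7 | 0.56 | 1.00 | 70.2 | 43 | 91.6% | 82.4% |

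The last two rows show how quickly the gain disappears once Screening is the weaker predictor.

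**Covariate or average?** With a = 0.8, b = 0.7, s = 0.6, entering both readings separately gives VR 0.99. Adjusting for their mean gives [1 − (b + s)²/(2(1 + a))] / (1 − b²) = [1 − 1.69/3.6] / 0.51 = 1.04, a loss. A separate coefficient lets a poor reading be down-weighted; averaging does not.

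**Primary endpoint.** With 45 per arm, delta 10 and SD 7.5, power at 0.05 is above 99.9% already. The possible benefit is a confidence interval narrower by the factor √VR, at best √0.83 = 0.91, about 9%.

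**The case against.** The strongest reply is that the gain may be nil, because the documents mark Screening as the less comparable reading. Experienced sites "may use this option instead of an arterial blood gas sample at Screening (Visit 1), Weeks 4 and 12 (Visits 3 and 5"), while arterial sampling is mandatory at Baseline and Week 24. Protocol 10.1.1 ties the oxygen flow at later blood gases to Baseline, not to Screening. Protocol 10.1.3 builds an oxygen titration into the Screening walk for subjects who need oxygen at rest. SAP 3.1 shows that protocol versions before 4.0 stratified by whether a lavage took place between screening and randomisation; for such a subject the two readings straddle a lavage. All of this stands, and is why the range must reach 1.00. It limits the gain but introduces no bias.

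A reader might infer that the trial is underpowered for 6MWD. The documents do not support that: the plan's criterion was 90% power at two-sided 5%, and 45 per arm gives 91.6%. The 0.0167 level governs 6MWD only if it has the smallest of the three p-values and the other two miss their own levels.

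A reader might also infer that the change raises power for the primary endpoint. On the plan's own delta and SD there is no power left to gain.

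Finally, the edit goes beyond the ANCOVA sentence, since the MMRM and imputation models must match. That is correct and is counted in the cost below.

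**Conclusion.** The point holds as an efficiency improvement, not as an error. Two pre-randomisation readings are collected, one is modelled, and using the other would leave the endpoint and the treatment contrast unchanged. For 6MWD the benefit lies between nothing and about 4 percentage points of power at 0.05 (91.6% to 95.6%), or about 7 points at 0.0167 (82.4% to 89.5%). In sample-size terms that is 36 to 43 per arm for 90% power. For (A-a)DO2 it is at most a somewhat narrower interval.

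The omission and the direction are certain from the documents. The size is not: it rests on assumed correlations, a common slope for the Screening value, and Week 24 data on all 45 subjects per arm. It would be wrong to read the favourable end as a saving that the sponsor has forgone. That end needs Screening to predict Week 24 as well as Baseline does, and the two-week correlation to be no higher than the 24-week one.

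**What to change.** Before unblinding:

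- Keep change from Baseline (Visit 2) as the endpoint. In SAP 5.3.7 and 5.5, add the Screening 6MWD as a second continuous covariate beside Baseline, not averaged with it. Doing the same for (A-a)DO2 in SAP 5.3.6 is optional.
- If Screening is missing, set it to Baseline. Where Screening already replaces a missing Baseline, the two covariates coincide, which is harmless.
- Carry the Screening value into the MMRM and multiple-imputation models for the same endpoint. If (A-a)DO2 is included, this covers the re-imputation after rescue treatment too.
- List the change in SAP 5.1, because Protocol 12.1.5 and 12.1.6 define the model with one baseline value.

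To judge the gain first, refit the blinded re-estimation ANCOVA for the 51 subjects with Screening 6MWD added and compare the residual MSE with 4928.203. Any treatment effect stays in both residuals, so the blinded ratio would, if anything, understate the gain.

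The cost is about one degree of freedom in the ANCOVA. The MMRM gains one parameter, or five if both covariates are crossed with the three visits (six slopes instead of one). No new data are needed. The gain may be negligible where the Screening gas was capillary, the Screening walk included oxygen titration, or a lavage fell between the two visits.
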